5.7. Allergy Skin Testing

A Greer® Pick® device that has been immersed in a solution of allergen extract purchased from Stallergenes Greer is used to apply allergen epicutaneously by placing the device at a 45 degree angle to the skin and gently lifting up to create a skin prick. All testing instruments are single patient use. Each patient will undergo skin prick testing with the following allergen preparations: House Dust Mite (*D. farinae*), House dust mite p (*D. pteronyssinus*), Cockroach, Tree mix, Grass Mix, Weed Mix, Mold Mix 1, Mold Mix 2, Rat, Mouse, Guinea Pig, Rabbit, Cat and Dog. The allergens will be placed on the forearm. After 15 minutes, a research coordinator will compare the wheal size (a raised bump surrounded by red itchy skin) for each allergen to that of the negative and positive control (histamine). A positive skin test is defined by a 3 mm wheal greater than the

saline control. For a volunteer to be considered non-allergic, the histamine control must be reactive and all others must be negative.

5.9. Symptom Score (administered in person at study visits and by telephone for post-challenge observation):

Allergen Challenge Phone Follow Up Questionnaire: (24 hours post challenge)

When speaking with the subject, use the following script:

On a scale of 0 to 3, with 0=no symptoms, 1=mild symptoms, 2=moderate symptoms and 3=severe symptoms, please rate the severity of each of the following symptoms:

Waking up at night due to cough (0-3): _____

Shortness of Breath (0-3): _____

Cough at rest (0-3): _____

Cough with Exercise (0-3): _____

Wheeze at Rest (0-3): _____

Wheeze with Exercise (0-3): _____

Total _____

2. Do you have any health concerns since we saw you on the day of the challenge?
3. Have you needed to see a doctor for any reason since your last visit?
4. Have you need to use any over the counter medications?

If the symptom score is 6 (out of a possible 18), or if any single symptom is a 3, or if the answers to questions 2, 3, 4, or 5 are “yes”, then the subject will be offered the opportunity to come back to the laboratory for follow up assessment by a study physician.

5.10. Nasal Epithelial Lining Fluid (ELF) Collection:

ELF is obtained by spraying the nostril with 0.9% sterile, normal saline irrigation solution (about 100 µl per nostril) one time per nostril. One 10x55mm strip of filter paper, cut from Leukosorb paper (Pall Scientific, Port Washington, NY) on a laser cutter, is inserted into the anterior portion of each nostril. The nostrils are clamped shut using a padded nose clip for two minutes. Strips are then removed from the nostril and collected in 1.5ml tubes. They are then stored in strips in a -20°C freezer until elution. ELF strips will be analyzed for cytokines and other chemical mediators.

6 STATISTICAL CONSIDERATION

6.1. Primary Endpoint

The principal endpoint of this screening inhaled allergen challenge protocol will be to identify those subjects who experience a 15% or greater drop in FEV₁ from baseline within 3-10 hours after the EPR.

6.2. Secondary Endpoint

In addition to identifying subjects for participation in the planned studies of Anakinra vs placebo for mitigating features of asthma exacerbation, the additional purpose of this study is to determine if IL-1 β concentrations in the sputum at baseline before challenge are predictive of key asthma outcomes following inhaled allergen challenge

- 1) Baseline sputum IL-1 β concentration (pg/mL)
- 2) Asthma outcomes following allergen challenge as measured by:
 - a). maximum drop in %FEV1 during LPR
 - b). Change in methacholine reactivity from baseline pre-allergen measurement to 24 hours after allergen challenge.
 - c). exhaled nitric oxide (eNO) level
 - d). induced sputum:
 - i. Granulocyte (neutrophils/eosinophils) numbers and percentages
 - ii. Mucins (secretion of MUC5AC and MUC5B determined by Western blot and ELISA)

Exploratory Endpoints

Additionally, as exploratory endpoints, we will assess the effects of allergen challenge on markers of systemic inflammation and changes in inflammatory gene expression as described below:

- a). **venipuncture** for assessment of systemic inflammatory markers (CBC with differential for absolute neutrophil count and absolute eosinophil count), pro-inflammatory cytokine levels such as IL-1 β , IL-6, IL-8).
- b). **nasal ELF** for assessment of inflammatory mediators associated with allergen-induced airway inflammation.
- c). **gene array analysis** from blood and induced sputum at the baseline visit, again on the day of the challenge and, finally, at 24 hours post challenge. To identify signaling pathways potentially impacted by allergen challenge, we will use Nanostring® technology to measure differential expression of a panel of 594 immunology-related genes. This will be accomplished by collecting and isolating peripheral blood mononuclear cells from venous blood samples collected before allergen challenge, during allergen challenge, and 24 hours after allergen challenge.
- d). **heart rate variability** measurement via commercially-available monitor (Space Labs, Inc). We will identify if specific cardiac changes occur during allergen-induced asthma exacerbation.
- e). **environmental sensors** developed through the National Science Foundation-funded Center for Advanced Self-Powered Systems of Integrated Sensors and Technologies (ASSIST) program will be worn by participants during inhaled allergen challenge. These health and exposure tracker devices include an ECG chest patch and a wrist band that will measure Heart Rate, motion and ambient temperature and ozone concentration.

6.3. Statistical Methods

Our analytical plan was developed with [name], the biostatistician for the CEMALB who will oversee all statistical analysis. In all analyses, criterion for significance will be $p \leq 0.05$. All statistical estimates will be tabulated along with the corresponding confidence intervals.

Our primary endpoint is identification of subjects who achieve a $\geq 15\%$ fall in FEV₁ during hours 3-10 following allergen challenge. We will subtract the pre-allergen challenge %FEV₁ value from the post-allergen %FEV₁ value to make this determination.

For analysis of secondary endpoints, we will first use linear regression to determine if there is a linear relationship between baseline sputum IL-1 β concentration (pg/mL) and asthma outcomes (maximum fall in %FEV1 during LPR, methacholine reactivity defined by the dose required to produce a $\geq 20\%$ drop in FEV1, sputum granulocyte content both in terms of % of total cell count and cells/mg of sputum, exhaled nitric oxide concentration) following allergen challenge, adjusting for potential confounders. The point estimate and confidence interval will be reported for the effect of baseline sputum IL-1 β on asthma outcomes. If the normality assumption is violated or there exists a non-linear relationship, we will calculate the Spearman correlation coefficient between baseline sputum IL-1 β concentration and asthma outcomes.

For analysis of exploratory endpoints, we will use two sample comparison tests to compare systemic inflammatory markers and gene expression levels before and after allergen challenge. We will use two-sample t tests or Mann Whitney U tests depending on whether the normality assumption is met. The point estimate and confidence interval will be reported for mean changes. We will transform the data to achieve normality if needed. HRV endpoints are exploratory, as we do not know if there will be changes during bronchospasm.

As we have considered additional individuals in our sample size calculation, we do not anticipate missing data will be a major issue affecting our study power.

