4. STUDY PROCEDURES

4.1. Screening/Baseline Visit Procedures:

Potential participants will be initially screened for eligibility through a separate screening protocol (IRB#98-0799).

Within 12 months of completing the screening protocol, they will return for Visit 1. Sensitization to cat as determined by skin testing or IgE levels is not expected to change over the course of 12 months. Participants will have to meet all eligibility criteria at the time of the Baseline Visit. On Visit 1:

1. Consent will be obtained
2. Review of subject's medical history and current medications. Allergy skin prick test results from screening protocol #98-0799 will be included in the history.
3. Vital sign measurements (temperature, pulse, respiratory rate, blood pressure), oxygen saturation, and symptom scoring
4. Urine pregnancy test for women of child bearing potential
5. eNO
6. Spirometry
7. Venipuncture for CBC with Diff, Total and cat hair IgE, cytokines, and gene expression (approximately 50 cc total)
8. Physical exam of the ears, nose, throat and chest
9. Sputum induction
10. Collect nasal epithelial lining fluid (ELF).

After completion of the baseline visit, and if for any reason that subject cannot return for the challenge session in the required time, a repeat baseline visit will be done. At this visit the subject will repeat the following:

1. review history and meds
2. vitals

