4.2. Intervention/Treatment procedures

Visit 2: Methacholine Challenge Day (at least 2 days but less than 2 weeks after the baseline visit V1)

1. Review any change in medical status since last visit
2. Vital signs, oxygen saturation, and symptom score
3. Urine pregnancy test
4. Baseline HRV measurement
5. eNO
6. Spirometry
7. Physical exam of the ears, nose, throat and chest

8. Methacholine challenge if inclusion and exclusion criteria are still met (refer to section 5.4 for methacholine challenge procedure)

Visit 3: Allergen challenge day (24-48 hours after V2)

1. Review any change in medical status since last visit
2. Vital signs, oxygen saturation, and symptom score
3. Placement of the HRV device
4. Placement of the ASSIST devices (cardiac electrodes and wrist band)
5. eNO
6. Collect nasal ELF
7. Spirometry
8. If inclusion and exclusion criteria are still met, allergen challenge will be performed as described in section 5.1.
 - a. If subject is asymptomatic and FEV1 drops $<10\%$ at the completion of allergen challenge, subjects will be monitored for 2 hours post challenge and will be discharged following post-challenge venipuncture with rescue medications (albuterol with aerochamber and oral prednisone 60 mg), instructions for use of these medications if asthma symptoms occur, and contact information for the on-call physician. Subject will resume protocol beginning with Study visit 4 detailed below.
 - b. Any subject whose FEV1 drops $\geq 10\%$ will stay for the 10 hour post-allergen monitoring period as outlined below.
9. Collect nasal ELF after completion of the allergen challenge, either following the dose producing a 20% or greater fall in FEV1 (in early phase responders) or following completion of the highest dose of inhaled allergen (in those who do not exhibit an early phase response).
10. Post-challenge monitoring of vital signs every 10 minutes for the 1st hour, then every 30 minutes until 2 hours post-challenge, then hourly until 10 hours post-challenge
11. Spirometry when vital signs are obtained
12. eNO hourly between 2 and 10 hours post-challenge
13. Collect nasal ELF at 7 hours post-challenge (7 hours after the onset of the early phase response).
14. Venipuncture for CBC with diff, cytokines, and gene expression 10 hours post-challenge (approximately 50 cc total)

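### Section 6.3 uses unpaired tests on before/after data from the same subjects, and judges a 594-gene panel at p ≤ 0.05 with no multiplicity control; both need correcting together.

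*Combined protocol and SAP*

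**What the plan says.** Section 6.3 sets one threshold for everything: "In all analyses, criterion for significance will be" p ≤ 0.05. For the exploratory endpoints it will "compare systemic inflammatory markers and gene expression levels before and after allergen challenge", and it names the tests: "We will use two-sample t tests or Mann Whitney U tests depending on whether the normality assumption is met". It adds: "The point estimate and confidence interval will be reported for mean changes".

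The exploratory endpoints in section 6.2 include using an array to "measure differential expression of a panel of 594 immunology-related genes". Samples are to come "from blood and induced sputum at the baseline visit, again on the day of the challenge" and at 24 hours.

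Section 3.1 describes a single-arm study. Under sections 4.1 and 4.2 the same subjects give blood for gene expression at Visit 1 ("Venipuncture for CBC with Diff, Total and cat hair IgE, cytokines, and gene expression"), at 10 hours on challenge day, and at Visit 4.

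No section gives a false discovery rate, a familywise rule, a gene filter or a pathway-level test, and none says that gene p-values are descriptive only.

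**The concern.** There are two faults, and they interact.

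- **The tests do not match the data.** Two-sample t and Mann-Whitney tests assume independent groups. Here there is one group measured twice, and the mean change that section 6.3 promises to report is a within-subject quantity. If a subject's two values are positively correlated, the unpaired test overstates the standard error. It then rejects less often than 5% under the null and loses power. This affects the systemic markers as well as the genes.
- **The gene panel has no multiplicity control.** Several hundred tests per contrast are each judged at 0.05, so the share of the flagged list that is due to chance is not controlled.

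The unpaired tests partly hide the second fault by being conservative. Correcting only the first exposes the second in full. Adding multiplicity control to the unpaired tests removes most of the remaining power in most of the cases examined. At stake is how far the gene list can be read as evidence of pathways affected by allergen challenge.

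**Working it through.** **From the documents.** 594 genes (6.2); threshold 0.05 (6.3); unpaired tests (6.3); same subjects before and after (3.1, 4.1, 4.2); up to 100 screened to find 25 late-phase responders (3.2, 6.4), so 25 to 100 subjects is used as the range.

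**Assumed, not in the documents.** Two-sided tests; gene-by-gene testing, as the named tests imply; rho from 0 to 0.7; 10 to 200 truly changed genes (k); effects for which a paired test has 80% power; equal variances; independent genes. Correlation between genes alters the spread of the null count, not its mean.

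The plan states no expected count, so there is no plan figure to reproduce.

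**Step 1, nominal size.** 594 × 0.05 = 29.7 genes per contrast if none changes (central 95% range 20 to 41).

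**Step 2, unpaired size.** The unpaired test takes the variance of the mean difference as 2σ²/n; the true value is 2σ²(1 − rho)/n. Under the null the statistic has standard deviation √(1 − rho), so the large-sample size is 2Φ(−1.96/√(1 − rho)). At rho 0.5 this is 2Φ(−2.77) = 0.0056, and 594 × 0.0056 = 3.3.

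**Step 3, unpaired power.** An effect with 80% paired power shifts the paired statistic by 1.96 + 0.84 = 2.80. Unpaired power is Φ(2.80 − 1.96/√(1 − rho)). At rho 0.5 this is Φ(0.03) = 51%.

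**Step 4, false share of the list.** (594 − k) × size / [(594 − k) × size + k × power]. At rho 0.3 and k = 30: 564 × 0.0191 = 10.8 false and 30 × 0.677 = 20.3 true, so 10.8/31.1 = 35%.

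| rho | size | chance genes if none changes | power | false share, k = 10 / 30 / 100 / 200 |
|---|---|---|---|---|
| 0 (or paired) | 0.0500 | 29.7 | 80% | 78 / 54 / 24 / 11% |
| 0.2 | 0.0284 | 16.9 | 73% | 69 / 42 / 16 / 7% |
| 0.3 | 0.0191 | 11.4 | 68% | 62 / 35 / 12 / 5% |
| 0.5 | 0.0056 | 3.3 | 51% | 39 / 17 / 5 / 2% |
| 0.6 | 0.0019 | 1.2 | 38% | 23 / 9 / 2 / 1% |
| 0.7 | 0.0003 | 0.2 | 22% | 8.5 / 3 / 0.8 / 0.3% |

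**Step 5, finite samples.** Simulation with 25, 50 and 100 subjects gave 17 to 18, 11 to 12, and 3.5 to 4.2 chance genes for the unpaired t test at rho 0.2, 0.3 and 0.5. Mann-Whitney gave similar counts (16.5 to 18, 11 to 13, 3.7 to 5.0). The paired t test gave 29 to 30 throughout.

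**Step 6, the alternatives.** Expected true / false genes declared per contrast (Benjamini-Hochberg rows by simulation, 6,000 runs):

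| Method | k = 30 | k = 100 |
|---|---|---|
| Plan, rho 0.2 | 22 / 16 | 73 / 14 |
| Plan, rho 0.3 | 20 / 11 | 68 / 9 |
| Plan, rho 0.5 | 15 / 3 | 51 / 3 |
| Paired, unadjusted | 24 / 28 | 80 / 25 |
| Paired, FDR 5% | 9 / 0.5 | 48 / 2.1 |
| Paired, FDR 10% | 12 / 1.4 | 60 / 5.6 |

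With k = 10, the paired tests declare about 2.0 true genes at FDR 5% and 2.7 at FDR 10%. If Benjamini-Hochberg is put on the unpaired tests instead, power at k = 30 and FDR 5% is about 12%, 6% and under 1% at rho 0.2, 0.3 and 0.5.

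**Step 7, the contrasts.** Section 6.2 names sputum on challenge day. Section 4.1, the Visit 4 list in 4.2 and the table in 15.1 place sputum induction only at Visits 1 and 4. At most one sputum contrast, baseline against 24 hours, is therefore possible.

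**The case against.** The strongest defence has four parts.

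1. **The endpoint is exploratory.** This is true and it lowers the severity. But the 0.05 rule is written for all analyses, and the label controls no error rate.
2. **At higher rho the unpaired tests yield few chance genes.** This also stands: 1.2 at rho 0.6 and 0.2 at rho 0.7. The price is power of 38% and 22% where a paired test has 80%, so high rho changes the fault without removing it.
3. **A screen may prefer finding true genes to limiting false ones.** That is partly a matter of preference, and adjustment does cost true genes. At rho 0.5 with 100 changed genes the plan gives 51 true and 3 false, close to the 48 true and 2.1 false under paired tests at FDR 5%. Since neither rho nor the number of changed genes is known beforehand, the plan cannot rely on being in that case.
4. **Section 6.3 promises estimates with confidence intervals.** If these were tabulated for every gene, a reader could approximate p-values and apply an adjustment. That helps only if the intervals are paired. An interval from the two-sample formula is too wide by 1/√(1 − rho), which is 1.41 at rho 0.5.

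A reader might also infer that early-discharge samples are mixed with the 10-hour samples in the gene analysis. The documents do not support that. For subjects who leave early, section 4.2 says only that "subjects will be monitored for 2 hours post challenge and will be discharged following post-challenge venipuncture", and section 4.8 is no more specific. Gene expression is named only for the 10-hour draw.

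**Conclusion.** The point holds. The certain error is the unpaired test on paired data; the missing multiplicity rule comes second, and the two have to be handled together.

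Over rho 0.2 to 0.7 and 10 to 200 changed genes, the false share of the list runs from under 1% to about 70%, and power runs from 73% down to 22%. These figures rest on the assumed rho, number of changed genes, 80% paired power and independence between genes. Only the 594 genes, the 0.05 threshold and the named tests come from the documents.

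A reader might infer that the plan will produce about 30 false genes per contrast. The documents do not support that: 29.7 applies to the named tests only if rho is about 0. It is otherwise the count after pairing without adjustment.

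Severity is minor to moderate. The primary endpoint, the sample size, the safety rules and selection for the anakinra trials do not depend on the gene results.

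**What to change.** Amend section 6.3, adopting parts 1 and 2 together.

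1. Use the paired t test or the Wilcoxon signed-rank test for every before/after exploratory comparison, systemic markers included, with paired confidence intervals.
2. For the gene panel, apply Benjamini-Hochberg to the paired p-values within each tissue and time contrast, at a false discovery rate fixed before analysis (for example 10%). Report raw p-values, estimates and intervals alongside as descriptive. Do not apply the adjustment to the unpaired tests.
3. List the contrasts. Reconcile section 6.2 with sections 4.1, 4.2 and 15.1 on sputum, and state whether sputum is assayed for gene expression. If early-discharge draws are assayed, do not pool them with the 10-hour draws.

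The cost is a short paragraph and a code change, with no new data. Subjects lacking one of the two samples drop out of that contrast. The main downside is fewer true genes declared than with unadjusted tests: at FDR 10%, about 2.7 of 10, 12 of 30 or 60 of 100 truly changed genes. Showing the unadjusted results beside the adjusted ones softens that loss.

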Statistical And Analytic Plan	
Our analytical plan was developed with [name], the biostatistician for the CEMALB who will oversee all statistical analysis. In all analyses, criterion for significance will be $p \leq 0.05$.
 
Our primary endpoint is identification of subjects who achieve a $\geq 15\%$ fall in FEV₁ during hours 3-10 following allergen challenge. We will subtract the pre-allergen challenge %FEV₁ value from the post-allergen %FEV₁ value to make this determination.
 
For analysis of secondary endpoints, we will first use linear regression to determine if there is a linear relationship between baseline sputum IL-1β concentration (pg/mL) and asthma outcomes (maximum fall in %FEV₁ during LPR, methacholine reactivity defined by the dose required to produce a $\geq 20\%$ drop in FEV₁, sputum granulocyte content both in terms of % of total cell count and cells/mg of sputum, exhaled nitric oxide concentration) following allergen challenge, adjusting for potential confounders. The point estimate and confidence interval will be reported for the effect of baseline sputum IL-1β on asthma outcomes. If the normality assumption is violated or there exists a non-linear relationship, we will calculate the Spearman correlation coefficient between baseline sputum IL-1β concentration and asthma outcomes.

DATA AND SAFETY MONITORING PLAN	We will use the NC TraCS DSMB to assess for possible changes to the overall risk of the study using inhaled allergen challenge. The DSMB will have full access to research records and source documents. Data regarding unanticipated problems will be provided to them as it is reported to the IRB and to the FDA. They will

review all adverse events, enrollment, and protocol deviations after the first 6 subjects have completed the inhaled allergen protocol, and then every 6 months thereafter. Any serious adverse events or major protocol deviations will be reported immediately to the DSMB via email, which may lead to an earlier review. They will communicate with the PI and the appropriate NIH Medical Officer regarding any safety issues.

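### The secondary IL-1β question is tested on 5 to 9 outcomes, each at p ≤ 0.05, with no lead outcome, adjustment or exploratory label

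*Combined protocol and SAP*

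**What the plan says.** The primary endpoint (sections 2.1 and 6.1) identifies subjects with a late phase response (LPR). It is a classification, and no hypothesis test is attached to it. The inferential question outside the exploratory list is the secondary one in section 6.2: whether baseline sputum IL-1β concentrations "are predictive of key asthma outcomes following inhaled allergen challenge".

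Section 6.3 gives the method: "For analysis of secondary endpoints, we will first use linear regression to determine if there is a linear relationship between baseline sputum" IL-1β and the asthma outcomes, with Spearman correlation as the fallback. The outcomes named there begin with "maximum fall in %FEV1 during LPR, methacholine reactivity defined by the dose required to produce a" 20% or greater FEV1 drop, and continue with "sputum granulocyte content both in terms of % of total cell count and cells/mg of sputum, exhaled nitric oxide concentration". Section 6.2 is more specific on cells, "Granulocyte (neutrophils/eosinophils) numbers and percentages", and adds the mucins MUC5AC and MUC5B, which section 6.3 does not mention. The same section 6.3 states that "In all analyses, criterion for significance will be" p ≤ 0.05. The synopsis repeats both the rule and the regression plan.

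Point estimates and confidence intervals are also promised. The exploratory label is applied to blood markers, nasal fluid, gene expression, heart rate variability and sensors, but not to the IL-1β outcomes.

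**The concern.** One question, whether IL-1β is predictive, is put to several outcomes at the full 0.05 level each. The plan does not say which outcome decides or how many must succeed, and it does not call the p-values descriptive. Under its own rule, any single significant regression can be reported as evidence of prediction. Different outcomes can also disagree, with nothing in the plan to settle the matter. Because the plan uses the exploratory label elsewhere, a reader will take these tests as formal ones. At stake is the reliability of a published statement about IL-1β; section 13 plans a manuscript.

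The outcome list is itself not fixed. Sections 6.2 and 6.3 differ on the mucins and on how far granulocytes are split. The eNO outcome has no stated time, although section 4.2 schedules "eNO hourly between 2 and 10 hours post-challenge" as well as a reading at Visit 4.

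**Working it through.** **The plan's own figures.** The documents state no family-wise error rate, so there is none to reproduce. The sizing in section 6.4 concerns other things: 100 × 0.50 × 0.50 = 25 LPR subjects, and 6.4 / 0.75 / 0.75 = 11.4, rounded up to 12 per anakinra protocol. Neither figure was derived from the IL-1β regressions.

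**Number of tests, k.**
- Section 6.3 with granulocytes pooled: LPR fall, methacholine, eNO, granulocyte %, granulocytes per mg = 5.
- With the cell types of section 6.2 kept separate: 1 + 1 + 1 + (2 cell types × 2 scales) = 7.
- Adding MUC5AC and MUC5B from section 6.2: 7 + 2 = 9.

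**Independent outcomes.** Chance of at least one false positive = 1 − 0.95^k:
- k = 5: 1 − 0.774 = 22.6%
- k = 7: 1 − 0.698 = 30.2%
- k = 9: 1 − 0.630 = 37.0%

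**Correlated outcomes.** The documents give no between-outcome correlation, so a range was simulated. One predictor unrelated to anything was regressed against k normal outcomes sharing a common correlation, with a two-sided test at 0.05 for each. There were 40,000 runs at sample sizes of 25 and 100, and the two sizes agreed within about 0.01.

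| Common correlation | k = 5 | k = 7 | k = 9 |
|---|---|---|---|
| 0 | 23% | 30% | 37% |
| 0.3 | 21% | 27% | 33% |
| 0.5 | 18% | 23% | 27% |
| 0.8 | 13% | 15% | 17% |

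If only the naturally paired measures (cell type on two scales, the two mucins) correlate at 0.8 and the rest are independent, the rates are 27.5% for k = 7 and 32.9% for k = 9.

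**Expected number of false positives.** This is 0.05 × k whatever the correlation: 0.25, 0.35 and 0.45.

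**Per-test level that holds 5% overall.** 0.05 / k = 0.010, 0.0071 and 0.0056. These are also the smallest Holm thresholds.

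The calculation assumes two-sided tests (the plan does not state sidedness), normal outcomes and no confounder adjustment. It does not count the Spearman fallback.

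**The case against.** The case for leaving the plan alone has substance. This is an open-label, single-arm screening study sized for other purposes, and family-wise control of secondary associations in such a study is partly convention. The plan sets 0.05 per analysis and never promises 5% across the family. It also commits to estimates with intervals. All of that is true and limits the weight of the point. It does not remove it: unadjusted intervals carry the same multiplicity, and the significance rule is stated for all analyses without qualification.

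Several stronger readings are tempting, and the documents do not support them.
- A reader might quote 23–27% as the error rate. That requires every pair of outcomes to correlate at about 0.5, which the documents do not say.
- A reader might treat 7 tests as the minimum. Section 6.3 speaks only of granulocyte content, so 5 is a fair reading.
- A reader might count each post-challenge eNO reading as a test: 9 hourly values, Visit 4 and the discontinuation visit make 11, and 9 − 1 + 11 = 19 tests. Section 6.3 names one eNO outcome and plans no such series. The missing time is an underspecified endpoint, not 11 planned tests.
- A reader might infer that a false IL-1β finding would affect the anakinra trials. Section 6.4 says those protocols are already developed, and entry rests on the LPR and the safety criteria of section 4.8, not on IL-1β.

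Making maximum LPR fall a gate for every other outcome is also open to objection. Under sections 4.2 and 4.8, subjects without symptoms and with an FEV1 fall below 10% leave after 2 hours and so have no 3–10 hour spirometry. Their Visit 4 sputum, eNO and methacholine remain scheduled. The gate would be missing in a subset selected by response.

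**Conclusion.** The point holds. As written, the plan applies p ≤ 0.05 to 5, 7 or 9 regressions that answer one declared secondary question, with nothing to limit or qualify a positive claim. If IL-1β predicts nothing, the chance of at least one significant result is about 13–23%, 15–30% or 17–37% respectively. The lower ends assume a common correlation of 0.8 and the upper ends assume independence. Every setting examined is well above 5%.

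The exact figure cannot be fixed from the documents, because it depends on the outcome count and on correlations they do not give. The primary purpose of identifying LPR subjects is unaffected. The correction is cheap and worth making before analysis.

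**What to change.** In section 6.2, section 6.3 and the synopsis:

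1. Give one identical list of IL-1β outcomes. State whether neutrophils and eosinophils are analysed separately, whether the mucins are included and by which assay, and use one eNO outcome. The Visit 4 (24 h) reading is the natural choice, since it matches the 24 h sputum and methacholine. Show the hourly eNO values descriptively.
2. Restrict the sentence that applies p ≤ 0.05 to all analyses, so that it no longer licenses an unadjusted claim on each outcome.
3. Choose one of two rules. Either apply Holm adjustment across the listed outcomes before claiming that IL-1β is predictive, or state that these p-values are unadjusted and exploratory and report estimates with 95% confidence intervals and no significance claim.
4. A lead outcome is optional. If maximum LPR fall is chosen, state the analysis population, including how subjects discharged at 2 hours are handled.

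The cost is wording only, with no added data, visits or subjects. The downside is that fewer nominally significant results can be claimed: under Holm, the smallest p-value must reach about 0.010 with 5 outcomes, 0.0071 with 7 or 0.0056 with 9.
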